#### 9.3.2 Second Visit

Visit 2, Day 10 +/-5: Otoscopy is performed. The subjects will hand in the completed questionnaires given to them at the previous appointment. The investigator will review the questionnaires and inquire about AEs. Any AEs will be reported in the CRFs. A lab test will be made to test speech intelligibility with the FST.

Their hearing aids will be fit with either the IMD or RMD (depending on what they had for the first period). The investigator will make no fine tuning of the fittings. Gain and features will be set as prescribed by the software. They will be given a standardized questionnaire (IOI-HA) and a custom product questionnaire to fill out during the second period of the field trial. The HCP will review the questionnaires to ensure that the subjects understand their task. They will be scheduled for the Third Visit.

#### 9.3.3 Third Visit

Visit 3, Day 20 +/-5: Otoscopy is performed. The subjects will hand in the completed questionnaires given to them at the previous appointment. The investigator will review the questionnaires and inquire about AEs. Any AEs will be reported in the CRFs. A lab test will be made to test speech intelligibility with the FST.

The subjects will return the hearing aids. The subjects will complete a custom preference questionnaire about the experience with both field test periods. They will report which period of the field trial that they preferred.

They will be given the option to purchase hearing aids from the clinic where they were recruited.

### 10. SAFETY

### 10.1 Medical Device Category C Studies

All adverse events (AE) including all serious adverse events (SAE) are collected, fully investigated and documented in the source document and appropriate case report form (CRF) during the entire study period, i.e. from patient's informed consent until the last protocol-specific procedure, including a safety follow-up period. Documentation includes dates of event, treatment, resolution, assessment of seriousness and causal relationship to device and/or study procedure.

The information on AEs is systematically collected by the clinician at each study visit. They will follow the procedures outlined in SOP-Medical Device Incident Reporting. The subjects are asked to keep a diary and write down any unexpected events. During the regular clinic visits the subjects are then asked questions about the event to gather details and to determine the severity of the event. If a subject reports pain that results in the inability to use the device he will be withdrawn from the study in order to avoid any pain from using the device and to remove partial data from the study. For reports of pain caused by insertion or the dome itself, the problem can be addressed in the clinic. For example, a different style or size of dome can be placed on the hearing aid, and re-training of insertion can be performed with the subject to avoid wrong or forceful insertion of the device. For reported pain they will be advised to not wear the device for 24 hours before resuming use.

Foreseeable adverse events outlined in the risk management file include discomfort caused by the domes, domes or filters falling off in the ear, no amplification coming from the device causing alarms or traffic to not be heard by the subject, skin reaction if chemical profile of device is changed, maximum output of the device exceeding 132 dB SPL, battery exploding or catching fire, and the device affecting other medical devices worn by the subject. The incidence of all of these risks or adverse events is improbable. To mitigate the risk, the IFU describes how to insert the device, how to change the domes, and how to change a battery in case of no amplification. The IFU describes how to clean the device, domes, and filters in order to not introduce cleaning agents that might change the chemical profile of the hardware of the device. The labelling warns of the potential maximum output of the device. The IFU instructs the user to keep the device away from explosive environments, The IFU warns of interference with implantable devices.

10.1.1 Definition and Assessment of (Serious) Adverse Events and other safety related events Adverse Event (AE)

Any untoward medical occurrence, unintended disease or injury or any untoward clinical signs (including an abnormal laboratory finding) in participants, users or other persons whether or not related to the investigational medical device [ISO 14155: 3.2].

This includes events related to the IMD or the RMD and to the procedures involved. For users or other persons this is restricted to events related to the IMD.

#### Adverse Device Effect (ADE)

Adverse event related to the use of an investigational medical device [ISO 14155: 3.1].

This includes any adverse event resulting from insufficient or inadequate instructions for use, deployment, implantation, installation, operation, or any malfunction of the investigational medical device. This includes any event that is a result of a use error or intentional misuse.

#### AEs/ADEs include:

- Exacerbation of a pre-existing disease or condition.

- Increase in the frequency or intensity of a pre-existing episodic disease or medical condition.

- Any disease or medical condition detected or diagnosed after treatment with the study intervention device even though it may have been present yet undetected prior to the start of the clinical investigation.

- Any continuous persistent disease or symptoms present at baseline that worsen following the start of the clinical investigation.

- Events considered by the investigator to be related to any of the clinical investigation-mandated procedures.

- Abnormal assessments, e.g. physical examination findings, will be reported as AEs/ADEs if they represent a clinically significant finding that was not present at baseline or that has significantly worsened during the course of the clinical investigation.

- Test abnormalities will be reported as AEs/ADEs if they represent a clinically significant finding, symptomatic or not, which was not present at baseline or has significantly worsened during the course of the clinical investigation.

#### AEs/ADEs do not include:

- Pre-planned interventions or occurrences of endpoints specified in the CIP are not considered AEs/ADEs, if not defined otherwise.

- Unrelated medical or surgical procedures, e.g. surgery, endoscopy, tooth extraction, transfusion. However, the event leading to the procedure may be considered an AE. If this event is serious, the procedure will be described in the SAE/SADE narrative.

- Any pre-existing disease or medical condition that remains stable and does not worsen during the course of study participation.

- Situations in which an adverse change did not occur, e.g., hospitalizations for unrelated cosmetic elective surgery or for social and/or convenience reasons.

#### Serious Adverse Event (SAE)

Adverse event that:

- results in death, or
- led to a serious deterioration in health that either:
- results in a life-threatening illness or injury, or
- results in a permanent impairment of a body structure or a body function, or
- required in-patient or prolonged hospitalisation, or
- results in medical or surgical intervention to prevent life threatening illness, or
- led to fetal distress, death or a congenital abnormality or birth defect. [ISO 14155: 3.37].

This includes device deficiencies that might have led to a serious adverse event if a) suitable action had not been taken or b) intervention had not been made or c) if circumstances had been less fortunate. These are handled under the SAE reporting system. A planned hospitalization for preexisting condition, or a procedure required by the protocol, without a serious deterioration in health, is not considered to be a serious adverse event.

#### Device deficiency

Inadequacy of a medical device related to its identity, quality, durability, reliability, safety or performance, such as malfunction, misuse or use error and inadequate labelling [ISO 14155: 3.15].

#### Health hazards that require measures

Findings in the trial that may affect the safety of study participants and, which require preventive or corrective measures intended to protect the health and safety of study participants.

#### Severity of adverse events/adverse device effects

The severity of clinical AEs is graded on a three-point scale: mild, moderate and severe, and reported in the CRF. If the severity of an AE worsens during medical device administration, only the worst intensity should be reported on the CRF. If the AE lessens in intensity, no change in the severity is required.

**Mild**: Event may be noticeable to subject; does not influence daily activities; the AE resolves spontaneously or may require minimal therapeutic intervention;

**Moderate**: Event may make subject uncomfortable; performance of daily activities may be influenced; intervention may be needed; the AE produces no sequelae.

**Severe**: Event may cause noticeable discomfort; usually interferes with daily activities; subject may not be able to continue in the study; the AE produces sequelae, which require prolonged therapeutic intervention.

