#### 4.4 Safety Objectives

The study aims to validate the overall implementation of the IMD. The study will test for unexpected behavior from the IMD and new risk factors to ensure safety of the devices before they are released to the market.

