# 8. STUDY INTERVENTION

### 8.1 Identity of Investigationa | Products (medical device)

The treatment will be approximately 1 month of use overall with hearing aids. During half of this time the participants will use hearing aids programmed with the IMD and during the other half the hearing aids will be programmed with the RMD.

There are 2 field test periods planned. They will continue wearing the hearing aids throughout both field tests and only have them reprogrammed at Visit 2. There is no need for a washout period or breaks between the fittings because amplification from hearing aids do not induce a carry-over effect.

At the end of the trial, the participants will return all hearing aids. They will have the option to purchase hearing aids, but they will be new serial numbers and not the devices used during the trial.

[figure not shown]

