#### 11.4.6 Safety analysis

Safety analysis is foreseen to be accomplished with the AEs reported by the participants during the trial. Clinical judgement from the PI will be used for the safety evaluation.

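### For an adverse event that is ongoing at the Visit 2 refit and then worsens, the planned record cannot show under which fitting the worst grade arose, and no rule assigns events to a fitting

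*Protocol*

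**What the plan says.** Under the severity heading of Protocol 10.1.1: "If the severity of an AE worsens during medical device administration, only the worst intensity should be reported on the CRF". The next sentence covers improvement: "If the AE lessens in intensity, no change in the severity is required". Each AE therefore carries one grade, its worst.

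Protocol 10.1 lists what else is kept: "Documentation includes dates of event, treatment, resolution, assessment of seriousness and causal relationship to device and/or study procedure". It also says: "The information on AEs is systematically collected by the clinician at each study visit". A date on which the grade changed is not in the list, and neither is the fitting in use.

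On the design, Protocol 8.1 says: "They will continue wearing the hearing aids throughout both field tests and only have them reprogrammed at Visit 2". Sections 6.2.1 and 9.3.2 confirm that one group starts on the IMD, the other on the RMD, and that both switch at Visit 2.

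The safety objective (4.4) is: "The study will test for unexpected behavior from the IMD and new risk factors". Section 4.2 makes the search for unwanted IMD behaviour a second primary objective. The safety analysis (11.4.6) says: "Safety analysis is foreseen to be accomplished with the AEs reported by the participants during the trial", and adds the clinical judgement of the principal investigator. The SAP has no safety analysis.

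**The concern.** Keeping only the worst grade is a sensible economy when each participant has one treatment, because the worst grade can then belong only to that treatment. Here every participant has both, one directly after the other. An AE that begins in the first field period and is still present at Visit 2 belongs partly to each fitting. If it then worsens, the fitting in use at that moment is what a reader of the safety results would want to know, and it is not among the items to be recorded.

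At stake is the ability to describe severity separately for the two fittings, in a study meant as the last validation of the IMD before release. A cross-over allows a comparison within a person only if events can be placed in a period.

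**Working it through.** The documents attach no figure to this rule, so there is none to reproduce. The check has three steps.

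**1. What can be recovered from the record.** The onset date, the visit dates and the randomised sequence together give the fitting in use at onset. The resolution date shows whether the AE ran into the second period. Take two different histories in a participant who starts on the RMD (the days are illustrative):

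| History | Under RMD | Under IMD | Entry under the rule |
|---|---|---|---|
| A | mild from day 4 | severe from day 13 | start day 4, grade severe, resolved in period 2 |
| B | severe from day 4 | mild from day 13 | start day 4, grade severe, resolved in period 2 |

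The entries are identical, so the fitting under which the worst grade occurred cannot be recovered from them.

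**2. Whether another part of the plan supplies it.**
- Causality (10.1.1) is rated against the medical device or study procedure. It does not separate IMD from RMD.
- Serial numbers (12.1.1) do not help, because the same aids are reprogrammed (8.1).
- The AE description (9.2.4.1) covers duration, number of occurrences and discomfort, not the date of a grade change.
- The diary (10.1) is not among the form contents listed in 12.1.1. Follow-up findings may stay in source notes only (10.1.3), whereas the analysis uses files extracted from the database (12.2.3).
- The list of what counts as an AE includes: "Any continuous persistent disease or symptoms present at baseline that worsen following the start of the clinical investigation". Its reference point is the start of the investigation, not the Visit 2 refit.
- Section 11.4.6 and the SAP contain no rule for assigning an AE to a fitting, whether by onset or otherwise.

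**3. What would follow if AEs were tabulated by onset.** This is an assumption, since the plan does not say so. For one AE, mild in the first period and severe after Visit 2:

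| Sequence | Table by onset | With the change recorded |
|---|---|---|
| RMD then IMD | RMD severe 1, IMD 0 | RMD mild 1, IMD severe 1 |
| IMD then RMD | IMD severe 1, RMD 0 | IMD mild 1, RMD severe 1 |

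The first row understates the IMD and the second overstates it, so the two sequences err in opposite directions.

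**How often.** Let p be the share of participants with an AE that both spans Visit 2 and worsens afterwards. The documents give no value, so p = 2%, 5% and 10% are assumptions. With the minimum of 24 participants (11.2) split equally, 12 are in each sequence. The chance of at least one such AE among 12 is 1 − (1 − p)^12:
- p = 0.02: 1 − 0.98^12 = 0.22
- p = 0.05: 1 − 0.95^12 = 0.46
- p = 0.10: 1 − 0.90^12 = 0.72

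The expected numbers per sequence are 12 × p = 0.24, 0.6 and 1.2. Among all 24 the chance of at least one is 38%, 71% or 92%. That figure pools the two opposite errors, so the per-sequence figures are the ones to read.

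**The case against.** Several points on the other side are sound.

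- **Nothing is deleted.** The worst grade and the event and resolution dates stay on the form, and AEs are asked about again at Visit 3 (9.3.3). A reader might infer that worsening under the IMD leaves no trace in the IMD period. It does leave one: the grade, and the fact that the AE ran on. Only the date of worsening is missing.
- **No tabulation by onset is planned.** A reader might infer that such AEs are dated to the wrong fitting. The onset date is correct for onset, and the plan does not use it to assign a fitting. The misplacement in step 3 is conditional. What stands is that the plan gives no rule at all.
- **The AE definition is not contradicted.** The item on symptoms present at baseline concerns complaints that predate the investigation, so an AE beginning during the first field period falls outside it. The definition also lists exacerbation of a pre-existing condition, which on some readings could open a new entry. The text does not settle this.
- **The rule can be read per fitting.** The schedule marks the device as administered at both Visits 1 and 2, so worsening during administration could mean within each fitting. On that reading the problem does not arise. But the aids are worn throughout both periods, and four investigators could apply the sentence differently.
- **Other records exist.** Source notes, the diary and source verification of AEs for all participants (12.3) may hold the timing. The database audit trail (12.2.2) would show a grade overwritten between visits, though with the time of entry rather than the date of worsening. Nothing says that any of these feeds the analysis.
- **The form is an appendix that is not available.** It may contain a field for period or grade change.
- **The expected burden is small.** Section 10.1 calls the foreseeable events improbable, section 9.2.4 does not expect the listed unexpected events, both fittings are meant to give the same acoustic output, and no formal safety comparison is planned. This limits the weight but does not remove the gap, because unexpected IMD behaviour is what the trial is meant to look for.

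**Conclusion.** The point holds in a limited form. For an AE that is ongoing at Visit 2 and then worsens, the record as described does not identify the fitting under which the worst grade was reached, and neither protocol nor SAP says how AEs are assigned to a fitting. Severity and attribution by fitting are lost. The occurrence of the AE is not.

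A reader might also infer that one such event would change the reading of the synopsis endpoint on unexpected device-related AEs. It would not: that endpoint turns on whether an event occurs, and the event is on the form either way. What is affected is the objective of detecting unwanted IMD behaviour (4.2, 4.4).

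The practical weight is modest. The 22%, 46% and 72% rest entirely on assumed rates and an equal split of 24. The conclusion also assumes that the rule is read across both fittings and that the unseen form has no period or grade-change field.

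**What to change.** In Protocol 10.1.1, replace the worst-grade sentence with a rule suited to a cross-over:
- Report the worst intensity within each field period.
- For an AE ongoing at Visit 2, record its grade before the second fitting.
- If it worsens after the second fitting, enter a new record linked to the first, with the date of worsening, its own grade and its own causality rating.

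In Protocol 11.4.6, state that AEs are listed by the fitting in use at onset or at worsening. List events during the Visit 1 IMD screening separately, since the footnote to the study schedule (9.1) shows that all participants have that exposure whatever their sequence.

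The cost is a short rewording in each of the two sections and a link field on the AE form. No visit or procedure is added, because AEs are already asked about at Visits 2 and 3, and no clinical management changes. The one drawback is that a persistent AE can give two linked entries, so the tables should count participants as well as events. If the form already has a period field, or the per-fitting reading was intended, the sentence in 10.1.1 only needs to say so; the assignment rule in 11.4.6 is still needed.

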#### Causal Relationship of Adverse Events

A causal relationship towards the medical device or study procedure should be rated as follows:

- Not related: The event is definitely not associated with device application or with study procedures; a relationship can be ruled out.
- Possibly related: The relationship between device application or study procedures and the event is possible, but other causes cannot definitely be ruled out.
- Related: The event is definitely associated with device application or study procedures.

Device deficiencies that might have led to an SAE are always related to the medical device.

#### 10.1.2 Reporting of (Serious) Adverse Events and other safety related events

The following events are to be reported to the Sponsor within 24 hours upon becoming aware of the event:

- All SAEs
- Health hazards that require measures
- Device deficiencies

The Sponsor will evaluate SAEs with regard to causality and seriousness. Device deficiencies are assessed regarding their potential to lead to an SAE.

#### Reporting to Authorities:

In Category C studies it is the local Investigator's responsibility to report serious adverse events in Switzerland which are

- related or possibly related to the medical device under investigation
- related or possibly related to study procedures

within 7 days to the local Ethics Committee. The Sponsor-Investigator reports within the same timeline to Swissmedic (incl. events from abroad).

• Health hazards that require measures are reported within 2 days

All in the trial involved other Ethical Committees receive all mentioned reportable SAEs and health hazards having occurred in Switzerland via the Sponsor-Investigator within the same timeline. All participating investigators are informed regarding the occurrence of a health hazard.

#### Period ic safety reporting

In Category C studies a yearly safety update-report is submitted by the Investigator to the Ethics Committee and by the Sponsor-Investigator to Swissmedic.

#### 10.1.3 Follow up of (Serious) Adverse Events

The adverse event shall be followed by the PI until its resolution or until the adverse event is recognised as permanent or stable condition by the PI. Follow-up investigations may be necessary according to the PI's medical judgement. In this situation, the follow-up does not have to be documented in the CRF but must be noted in the source documentation.

In case of SAE / SADE the sponsor can be contacted following the list below. If the first person in the list cannot be timely contacted, the PI should try to contact the next and so on.

# **11. STATISTICAL METHODS**

The purpose of this study is to compare the performance of the IMD to the RMD. The study aims to provide a final validation and quality control of the IMD before it is released for sales. The hearing aids will have the same electro-acoustic characteristics with bot the IMD and the RMD. For this reason, it is not expected to find that the IMD outperforms the standard RMD.

### 11.1 Hypothesis

Both devices will have the same electro-acoustical performance; however, it is suspected that changing the fitting procedure might influence the subjective benefit for the hearing aid user. Research suggests that placebo effect might impact hearing aid trials (Dawes et al., 2013) and that clinician behavior might also modify the perceived benefit of hearing aids (Naylor et al., 2015). The designed test will investigate the potential effect of the IMD compared to the RMD on first time users.

The test should answer the following research questions:

- Narrative effect of fitting procedure: Do different fitting procedures lead to differences in perceived benefit with hearing aids despite similar electro-acoustical performance? (Questionnaires)
- 2. Self-administrated audiometry: Is AMTAS self-administrated screening equivalent to standard clinical procedure? (hearing loss thresholds)

